11.2 Subject demographics and other baseline characteristics

All data for background and demographic variables will be listed by treatment group and subject. Summary statistics will be provided by treatment group.

Relevant medical history, current medical conditions, results of laboratory screens, drug tests and any other relevant information will be listed by treatment group and subject.

11.3 Treatments

Data for study drug administration (rescue medication) and concomitant therapies will be listed by treatment group and subject.

11.4 Analysis of the primary variable(s)

The primary objective of this study is to assess the efficacy of 16 weeks of QCC374 administration in patients with PAH. The primary endpoint is the percentage of the baseline PVR at week 16.

11.4.1 Variable(s)

The primary variable is the PVR. The log transformed PVR is expected to be approximately normally distributed.

11.4.2 Statistical model, hypothesis, and method of analysis

The change from baseline (on log transformed values) will be analyzed using an ANCOVA model with treatment as a factor and log transformed baseline PVR as a covariate. Likelihood based posterior distributions will be derived to assess the probability that QCC374 is better than placebo and the probability that the reduction vs placebo is at least 15%.

Corporate Confidential Information

11.4.3 Handling of missing values/censoring/discontinuations

The primary analysis of efficacy will be conducted only on complete cases (i.e. patients with baseline and week 16 PVR values), which is considered valid under the missing completely at random (MCAR) assumption.

11.4.4 Sensitivity analyses

Sensitivity analyses will be carried out if the assumption of missing completely at random values is not appropriate.

11.5 Analysis of secondary variable(s)

11.5.1 Efficacy / Pharmacodynamics

For the 6MWD, mPAP, PCWP, CO, SVR, and RV function with echocardiography, the raw data and change from baseline will be listed by treatment, subject and visit/time. Summary statistics will be provided by treatment and visit/time.

For the 6MWD, change from baseline will be analyzed using a mixed effects model for repeated measures. The model will investigate effects for treatment by time interaction and baseline by time interaction. The outcome of interest will be the comparison of QCC374 versus placebo after 16 weeks of treatment.

The mPAP, PCWP, CO, SVR, and RV function parameters with echocardiography will be analyzed using ANCOVA model with treatment as a factor and baseline value as a covariate. If the distribution of a variable cannot be assumed normal, log-transformation or a non-parametric test will be used.

11.5.2 Safety

Vital signs

All vital signs data will be listed by treatment, subject, and visit/time and if ranges are available abnormalities (and relevant orthostatic changes) will be flagged. Summary statistics will be provided by treatment and visit/time.

ECG evaluations

All ECG data will be listed by treatment, subject and visit/time, abnormalities will be flagged. Summary statistics will be provided by treatment and visit/time.

Clinical laboratory evaluations

All laboratory data will be listed by treatment, subject, and visit/time and if normal ranges are available abnormalities will be flagged. Summary statistics will be provided by treatment and visit/time.

Adverse events

All information obtained on AEs will be displayed by treatment and subject.

The number and percentage of subjects with AEs will be tabulated by body system and preferred term with a breakdown by treatment. A subject with multiple adverse events within a body system is only counted once towards the total of this body system.

Spirometry

All spirometry data will be listed by treatment, subject and visit/time. Summary statistics will be provided by treatment and visit/time.

Pharmacokinetics

QCC374 and QCM441 plasma concentration data will be listed by dose-level, subject, and visit/sampling timepoint. Missing data will be labeled as such in the concentration data listings.

Descriptive summary statistics will be provided by dose-level and visit/sampling time point, including the frequency (n, %) of concentrations below the LLOQ and reported as zero. Summary statistics will include mean (arithmetic and geometric), SD, CV (arithmetic and geometric), median, minimum and maximum. Concentrations below LLOQ will be treated as zero in summary statistics as well as for calculation of PK parameters. A geometric mean will not be reported if the dataset includes zero values.

Pharmacokinetic parameters will be calculated as described in [Section 8.7](#) and will be listed by dose-level, study day and subject. Descriptive summary statistics will be provided including mean (arithmetic and geometric), SD, CV (arithmetic and geometric), median, minimum and maximum. An exception to this are T_{max}, T_{min}, and T_{last} where only median, minimum and maximum will be presented. A geometric mean will not be reported if the dataset includes zero values.

11.5.3 Pharmacokinetic / pharmacodynamic interactions

Not applicable for this study.

11.5.4 Other assessments

There will be no other assessments than what has been previously documented.

Corporate Confidential Information

11.7 Sample size calculation

We assume around 20% dropout, which should provide complete PVR data from around 30 patients (approximately 10 on placebo and approximately 20 on QCC374), if approximately 38 patients are randomized. Corporate Confidential Information

Corporate Confidential Information

If the true effect is 20% over placebo, then the probability to meet the efficacy criteria is 80%.
If the drug effect over placebo is 0, then there is 40% chance of declaring futility at the IA.
If the drug effect over placebo is 0, then the chance of declaring efficacy is 9% at the end of the study.

Corporate Confidential Information

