Purpose and rationale	This study is designed as a proof of concept study for QCC374, an inhaled prostacyclin receptor (IPR) agonist for the treatment of PAH. The purpose of this study is to assess the safety, tolerability, pharmacokinetics and efficacy of QCC374 in adult patients with PAH to determine if QCC374 has an adequate clinical profile to warrant further clinical development in this indication.
Primary Objective(s)	To assess the efficacy of 16 weeks of QCC374 administration in patients with PAH by measuring the change from baseline in pulmonary vascular resistance (PVR).
Secondary Objectives	
 • To evaluate the safety and tolerability of multiple doses of QCC374 in patients with PAH • To evaluate the preliminary efficacy of 16 weeks of QCC374 administration in patients with PAH by measuring changes from baseline in: 
 • Six minute walk distance (6MWD) • Hemodynamic parameters other than PVR • Right ventricular function with echocardiography • To evaluate the pharmacokinetics of QCC374 and its metabolite QCM441 in patients with PAH
Study design	
This is a non-confirmatory, randomized, subject and investigator blinded, placebo controlled study of QCC374 in PAH patients. The study will have 2 parts. In Part 1, an initial safety cohort, 8 subjects will be randomized in a 6:2 ratio and the starting dose will be 0.03 mg bid. In Part 2, ~ 30 subjects will be randomized in a 2:1 ratio, with a starting dose of 0.03 mg bid. In Part 1, subjects will be up-titrated during the first two weeks of the study to 0.12 mg bid, or to their maximum tolerated dose (MTD) if their individual MTD is below 0.12 mg bid during the first two weeks of the study.
 
In Part 2, subjects will be up-titrated during the first two weeks of the study to 0.06 mg bid, or will remain at the starting dose of 0.03 mg bid if the investigator believes, based on their medical judgement, that the dose should not be increased.
 
The treatment duration is 16 weeks.

Population	The study population for Parts 1 and 2 will be comprised of male and female adults with symptomatic PAH. A total of approximately 38 patients are planned to be enrolled and randomized, with approximately 30 patients expected to complete the study. The sample size will be re-estimated at the interim analysis and number of randomized patients may be increased up to a maximum of 60.

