Data analysis	
Data from the two parts of the study will be pooled for the statistical analysis.
 
The primary variable is PVR. The log transformed PVR is expected to be approximately normally distributed. The change from baseline (on log transformed values) will be analyzed using an Analysis of Covariance (ANCOVA) model with treatment as a factor and log transformed baseline PVR as a covariate. Likelihood based posterior distributions will be derived to assess the probability that QCC374 is better than placebo and the probability that the reduction vs placebo is at least 15%.
 
The efficacy criteria at the end of the study is as follows:
 
 • If there is at least 90% probability that the treatment effect of QCC374 is better than placebo in PVR and • If there is at least 50% probability that the reduction in PVR is at least 15% in favor of QCC374 compared to placebo.
Key words	Pulmonary Arterial Hypertension, Prostacyclin

1 Introduction

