6.1.3 Statistical model, assumptions and hypotheses

The change from baseline (on log transformed values) will be analyzed using an ANCOVA model with treatment as a factor and log transformed baseline PVR as a covariate. Likelihood based posterior distributions, based on model adjusted means and assuming a t-distribution, will be derived to assess the probability that QCC374 is better than placebo and the probability that the reduction vs placebo is at least 15%.

The following criteria will be assessed as a guide to decision making:

Efficacy criteria at Interim analysis:

- If there is at least 90% probability that the treatment effect of QCC374 is better than placebo in PVR and
 - If there is at least 50% probability that the reduction in PVR is at least 15% (corresponding to a ratio of 0.85) in favor of QCC374 compared to placebo.
- Corporate Confidential Information

Corporate Confidential Information

Efficacy criteria at End of Study:

- If there is at least 90% probability that the treatment effect of QCC374 is better than placebo in PVR and
- If there is at least 50% probability that the reduction in PVR is at least 15% in favor of QCC374 compared to placebo.

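### Can the 80% and the 9% in protocol section 11.7 both hold under the two-part efficacy rule?

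*Protocol*

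**What the plan says.** Protocol section 11.7 starts from "We assume around 20% dropout", so about 38 randomized patients should yield about 30 with complete PVR data: "approximately 10 on placebo and approximately 20 on QCC374". It then gives three probabilities:

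- For power: "If the true effect is 20% over placebo, then the probability to meet the efficacy criteria is 80" (per cent).
- For stopping early: an inactive drug has a 40% chance of being called futile at the interim.
- For false positives: "If the drug effect over placebo is 0, then the chance of declaring efficacy is 9% at the end of the study".

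Text directly before and after these sentences is redacted.

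In the protocol's visible text the criteria appear only in the synopsis, introduced by "The efficacy criteria at the end of the study is as follows". There are two, and both must be met: at least 90% posterior probability that QCC374 beats placebo on PVR, and at least 50% posterior probability that the reduction against placebo is 15% or more. SAP 6.1.3 states the same pair for the end of the study and also under "Efficacy criteria at Interim analysis", followed by redacted text. The SAP describes the criteria as guiding decisions.

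The synopsis also says: "The sample size will be re-estimated at the interim analysis and number of randomized patients may be increased up to a maximum of 60".

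**The concern.** The 9% is tied in words to the end of the study. The 80% refers to criteria that the protocol visibly defines only for the end of the study. Taken together, the natural first reading is that both describe one test on the final data.

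On that reading the numbers cannot both be right. The posterior is centred on the estimate, so the 50% criterion amounts to requiring an estimated ratio of 0.85 or less. A true ratio of 0.80 lies close to that cut, while no effect lies far from it. A design precise enough to clear the cut 80% of the time at 0.80 should hardly ever clear it under no effect.

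If one of the figures were wrong, the sponsor could misjudge the risk of taking an inactive drug forward or dropping an active one. If both were right but cumulative over two looks, a reader who applied them to the final result alone would overstate both the power and the false-positive rate of that look.

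**Working it through.** **Inputs from the documents.** 20 versus 10 completers; true ratio 0.80 or 1.00; the two-part rule; 40% futility at the interim under no effect (all section 11.7, the synopsis and SAP 6.1.3). The analysis is on log PVR with t-based posteriors.

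**Inputs assumed.** The log-scale SD and the interim timing, which are redacted. Both were varied.

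**One final look.** ln 0.85 = −0.1625 and ln 0.80 = −0.2231, a gap of 0.0606. The standard error is SE = SD × √(1/20 + 1/10) = 0.387 × SD.

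- *Fix power at 80%.* SE = 0.0606 / 0.8416 = 0.0720, so SD = 0.0720 / 0.387 = 0.186. The 90% criterion needs an estimate below about −1.28 × 0.0720 = −0.092, so the 0.85 cut alone decides. The false-positive rate is Φ(−0.1625 / 0.0720) = 1.2%. This holds for any sample size, because only the SE enters.
- *Fix the false-positive rate at 9%.* SE = 0.1625 / 1.341 = 0.1212, so SD = 0.313. Power is Φ(0.0606 / 0.1212) = 69%. With t posteriors on 27 df, 9.0% is reached at SD 0.336, where power is 64%.

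In between, SD 0.24 gives 74.3% and 4.0%. No SD gives both 80% and 9%. Binding futility lowers both figures, so it does not help.

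**Final look only, with re-estimation.** Sixty randomized with 20% dropout leaves 60 × 0.8 = 48 completers. Even with the final size chosen after the interim in the way most favourable to success, power is at most about 77% when the false-positive rate is 8.5% to 9.5%. With 60 completers and no dropout, the same extreme rule reaches 77.6% to 79.1%, depending on how late an interim is allowed.

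**Success at the interim or the final look.** Simulation with t posteriors, 30 completers in total, and the futility cut set so that 40% stop under no effect:

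| Interim at (completers) | SD (assumed) | Power, either look | False positives, either look | Final look alone (power / false positives) |
|---|---|---|---|---|
| 15 | 0.23 | 81.3% | 9.5% | 75.2% / 3.4% |
| 18 | 0.24 | 80.3% | 9.2% | 74.3% / 4.0% |
| 20 | 0.24 | 80.0% | 8.5% | 74.1% / 4.0% |
| 21 | 0.25 | 79.0% | 8.9% | 73.4% / 4.6% |

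The rows at 18 and 20 completers come within about half a percentage point of both stated figures, and the other two within about 1.3 points. The fit depends on timing. At SD 0.24, an interim at 12 completers gives 79.4% and 11.0%, and one at 24 gives 79.2% and 6.8%. The last column only illustrates how the totals might split, since it rests on the assumed inputs.

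**The case for a change.** The strongest case for acting is that the one-look conflict needs no assumed SD: 80% power on the 0.85 cut forces about 1.2% false positives. The words attached to the 9% name the end of the study, and no visible sentence says that interim success counts. Under the reading that fits, the final look alone would have roughly 73% to 75% power and 3% to 5% false positives, so someone relying on the printed label would misjudge that look. Saying which looks are counted would take one phrase.

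The arithmetic stands, and the visible wording could be tighter. The inference that the plan is at fault does not stand, for three reasons.

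- The 9% sentence comes straight after the one on futility at the interim. The pair reads naturally as a sequential summary: the chance of stopping for futility at the interim, then the chance of having declared efficacy by the time the study is over. The 80% sentence does not mention the end of the study at all; that limit has to be imported from the synopsis.
- The SAP applies identical criteria at the interim, so counting success there follows from the plan's own rule.
- The SD, the interim timing and the futility and re-estimation rules fall in redacted text. They cannot be called missing, and that text may already define what is counted.

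The two-look reading is not proved to be the sponsor's. The 90% criterion alone, with binding futility and an early interim, also gives about 80% to 81% and 9.3% to 9.6% at SD 0.26. That reading drops half of the stated rule, so it is the less likely one.

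**Conclusion.** No change is needed. The 80% and the 9% cannot both describe a single final look at 20 versus 10 completers, but they agree with each other when success at the interim or the final look counts. That agreement needs a log-scale SD of about 0.23 to 0.25 and an interim at about 15 to 21 of 30 completers. Both are assumptions, though unremarkable ones, and the result supports the sponsor's figures.

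What remains is a loose phrase in the visible part of a partly redacted section. An analyst would take the figures as overall operating characteristics of the design. The trial is non-confirmatory, the criteria guide a decision, and the ANCOVA, the thresholds and the planned numbers are the same under either reading. Spelling out which looks are counted, or splitting the figures by look, would be a reporting preference and would not correct any result.

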11.8 Power for analysis of key secondary variables

Not applicable.

12 Ethical considerations

12.1 Regulatory and ethical compliance

This clinical study was designed and shall be implemented and reported in accordance with the ICH Harmonized Tripartite Guidelines for Good Clinical Practice, with applicable local regulations (including European Directive 2001/20/EC, US Code of Federal Regulations Title 21, and Japanese Ministry of Health, Labor, and Welfare), and with the ethical principles laid down in the Declaration of Helsinki.

12.2 Responsibilities of the investigator and IRB/IEC

Before initiating a trial, the investigator/institution should obtain approval/favorable opinion from the Institutional Review Board/Independent Ethics Committee (IRB/IEC) for the trial protocol, written informed consent form, consent form updates, subject recruitment procedures (e.g. advertisements) and any other written information to be provided to subjects. Prior to study start, the investigator is required to sign a protocol signature page confirming his/her agreement to conduct the study in accordance with these documents and all of the instructions and procedures found in this protocol and to give access to all relevant data and records to Novartis monitors, auditors, Novartis Quality Assurance representatives, designated

agents of Novartis, IRBs/IECs, and regulatory authorities as required. If an inspection of the clinical site is requested by a regulatory authority, the investigator must inform Novartis immediately that this request has been made.

For multi-center trials, a Coordinating Investigator will be selected by Novartis around the time of Last Patient Last Visit to be a reviewer and signatory for the clinical study report.

12.3 Publication of study protocol and results

Novartis assures that the key design elements of this protocol will be posted in a publicly accessible database such as clinicaltrials.gov. In addition, upon study completion and finalization of the study report the results of this trial will be either submitted for publication and/or posted in a publicly accessible database of clinical trial results.

13 Protocol adherence

This protocol defines the study objectives, the study procedures and the data to be collected on study participants. Additional assessments required to ensure safety of subjects should be administered as deemed necessary on a case by case basis. Under no circumstances should an investigator collect additional data or conduct any additional procedures for any research related purpose involving any investigational drugs.

Investigators must apply due diligence to avoid protocol deviations. If the investigator feels a protocol deviation would improve the conduct of the study this must be considered a protocol amendment, and unless such an amendment is agreed upon by Novartis and approved by the IRB/IEC/REB it cannot be implemented. All significant protocol deviations will be recorded and reported in the CSR.

Isolated ALP elevation	
 • Repeat liver chemistry tests within 48-72 hours • If elevation is confirmed, measure fractionated ALP; if >50% is of liver origin, establish hepatic causality • Complete CRFs per liver event guidance
Any AE potentially indicative of liver toxicity	
 • Consider study treatment interruption or discontinuation • Hospitalize if clinically appropriate • Complete CRFs per liver event guidance

Table 15-3 Exclusion of underlying liver disease

Disease	Assessment
Hepatitis A, B, C, E	
 • IgM anti-HAV; HBSAg, IgM anti-HBc, HBV DNA; anti-HCV, HCV RNA, IgM & IgG anti-HEV, HEV RNA
CMV, HSV, EBV infection	
 • IgM & IgG anti-CMV, IgM & IgG anti-HSV; IgM & IgG anti-EBV
Autoimmune hepatitis	
 • ANA & ASMA titers, total IgM, IgG, IgE, IgA
Alcoholic hepatitis	
 • Ethanol history, GGT, MCV, CD-transferrin
Nonalcoholic steatohepatitis	
 • Ultrasound or MRI
Hypoxic/ischemic hepatopathy	
 • Medical history: acute or chronic CHF, hypotension, hypoxia, hepatic venous occlusion. Ultrasound or MRI.
Biliary tract disease	
 • Ultrasound or MRI, ERCP as appropriate.
Wilson disease	
 • Caeruloplasmin
Hemochromatosis	
 • Ferritin, transferrin
Alpha-1-antitrypsin deficiency	
 • Alpha-1-antitrypsin

16 Appendix 2: Specific Renal Alert Criteria and Actions

Table 16-1 Specific Renal Alert Criteria and Actions

Criteria	Action required
Serum creatinine (sCr) increase 25 – 49% compared to baseline	
 Consider causes and possible interventions Follow up within 2-5 days
Serum creatinine increase $\geq 50\%$	
 Consider causes and possible interventions Repeat assessment within 24-48h if possible Consider drug interruption or discontinuation unless other causes are diagnosed and corrected Consider hospitalization and specialized treatment
Protein-creatinine or albumin-creatinine ratio increase ≥ 2 -fold or new onset dipstick proteinuria $\geq 1+$ or Albumin-creatinine ratio (ACR) ≥ 30 mg/g or ≥ 3 mg/mmol; or Protein-creatinine ratio (PCR) ≥ 150 mg/g or >15 mg/mmol	
 Consider causes and possible interventions Assess serum albumin & serum protein Repeat assessment to confirm Consider drug interruption or discontinuation unless other causes are diagnosed and corrected
New onset glucosuria on urine dipstick (unless related to concomitant treatment, diabetes)	
Assess & document:
 
 Blood glucose (fasting) Serum creatinine Urine albumin-creatinine ratio
New hematuria on dipstick	
Assess & document:
 
 Urine sediment microscopy Assess sCr and urine albumin-creatinine ratio Exclude infection, trauma, bleeding from the distal urinary tract/bladder, menstruation Consider bleeding disorder

Additional specialized assessments are available to assess renal function or renal pathology. Whenever a renal event is identified, a detailed subject history and examination are indicated to identify, document and potentially eliminate risk factors that may have initiated or contributed to the event:

- Blood pressure assessment (after 5 min rest, with an appropriate cuff size)
- Signs and symptoms such as fever, headache, shortness of breath, back or abdominal pain, dysuria, hematuria, dependent or periorbital edema
- Changes in blood pressure, body weight, fluid intake, voiding pattern, or urine output
- Concomitant events or procedures such as trauma, surgical procedures, cardiac or hepatic failure, contrast media or other known nephrotoxin administration, or other potential causes of renal dysfunction, e.g., dehydration, hemorrhage, tumor lysis

Table 16-2 Follow-up of renal events

Action	Follow up
Assess*, document and record in the Case Report Form (CRF) or via electronic data load. Review and record possible contributing factors to the renal event (co-medications, other co-morbid conditions) and additional diagnostic procedures (MRI etc) in the CRF.	
• Urine dipstick and sediment microscopy• Blood pressure and body weight• Serum creatinine, electrolytes (sodium, potassium, phosphate, calcium), bicarbonate and uric acid• Urine output
Monitor subject regularly (frequency at investigator's discretion) until:	
• Event resolution: (sCr within 10% of baseline or protein-creatinine ratio within 50% of baseline) or 
• Event stabilization: sCr level with $\pm 10\%$ variability over last 6 months or protein-creatinine ratio stabilization at a new level with $\pm 50\%$ variability over last 6 months.

* Urine osmolality: in the absence of diuretics or chronic kidney disease this can be a very sensitive metric for integrated kidney function that requires excellent tubular function. A high urinary osmolality in the setting of an increase in sCr will point toward a “pre-renal” cause rather than tubular toxicity.
